10.6.2. Study Population

Date of Birth

• Only the year of birth will be captured, and therefore the date of birth is then derived as follows: Year of birth = YYYY \rightarrow Date of birth = 30th June YYYY

Age

- - Calculated as the integer part of (date of screening date of birth)

Age = integer part (date of screening – 30th June YYYY) / 365.25.

• Birth date will be presented in listings as 'YYYY'.

Body Mass Index (BMI)

• Calculated as Weight (kg) / [Height (m) 2]

Treatment Compliance

Treatment compliance will be calculated based on the formula:

Treatment Compliance = Number of Actual Doses / (Planned Treatment Duration in Days * Frequency)

- Frequency is 2 for BID and 3 for TID. Treatment compliance could be greater than 100% if there are events of overdose. Cumulative compliance (since Day 1) at each visit will be calculated.
- Planned Treatment Duration is defined as 1 day in Part A in each period and 14 days in Part B.

Extent of Exposure

- Number of days of exposure to study drug will be calculated based on the formula: Duration of Exposure in Days = Treatment Stop Date – (Treatment Start Date) + 1
- Participants who were randomized but did not report a treatment start date will be categorised as having zero days of exposure.
- The cumulative dose will be based on the formula:

Cumulative Dose = Sum of (Number of Days x Total Daily Dose)

• If there are any treatment breaks during the study, exposure data will be adjusted accordingly.

205184

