12.9. Appendix 9: Protocol Amendment History

The Protocol Amendment Summary of Changes Table for the current amendment is located directly before the Table of Contents (TOC).

TITLE PAGE

Protocol Title: A single-centre, randomized, double-blind (sponsor-unblinded), placebo-controlled study to evaluate the safety, tolerability and pharmacokinetics of GSK2982772 in repeat oral doses in healthy subjects.

Protocol Number: 205184/ Amendment 02

Short Title: GSK2982772 high dose safety and PK study in healthy volunteers.

Compound Number: GSK2982772

Sponsor Name and Legal Registered Address:

GlaxoSmithKline Research & Development Limited
[name]
[name]
[name]
UK

Medical Monitor Name and Contact Information can be found in the Study Reference Manual

Regulatory Agency Identifying Number(s): EudraCT 2017-002662-45

Approval Date: 26-Feb-2018

SPONSOR SIGNATORY:

PPD

26th Feb 2018

[name], MBA
Vice President and Head Unit Physician
Immuno-Inflammation Therapy Area

Date

PPD

PROTOCOL AMENDMENT SUMMARY OF CHANGES TABLE

DOCUMENT HISTORY	
Document	Date
Amendment 02 Republishing	26-Feb-2018
Amendment 02	15-FEB-2018
Amendment 01	07-DEC-2017
Original Protocol	31-JUL-2017

Amendment 02 Republishing 26-Feb-2018

Overall Rationale for the Amendment:

Due to a number of asymptomatic, non-serious and self-limiting cardiac arrhythmias observed in Cohorts 1 and 2 prompting a temporary dosing hold, the 120 mg TID for 14 days will be repeated in Cohort 3. The randomization ratio has been changed to 9:5 (Active:Placebo) in the remaining Cohorts of Part B (Cohorts 3, 4 and 5) to provide a more balanced comparison between subjects on active and placebo. Furthermore, 24 hour Holter monitoring will now be conducted at the screening visit to better understand the background telemetry patterns of each subject prior to the start of dosing.

Two additional PK timepoints will be collected on Day 1 in Cohorts 3 and 4 to enable the C_{max} to be determined following the second dose of the day.

In addition, further administrative clarifications have been made.

Section # and Name	Description of Change	Brief Rationale

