
1. Protocol Synopsis for Study 205184
 
5.1. Overall Design
 
5.2. Number of Participants
 
5.3. Sentinel Dosing
 
5.6. Scientific Rationale for Study Design
 
7.2. Method of Treatment Assignment
 
10.2. Sample Size Sensitivity
	
The Study Design schematic has been updated to add Cohort 3 and adjust the randomization ratio from 3:1 to 9:5 in Cohorts 3, 4 and 5.
 
The Type and Number of Participants has been raised to 14 subjects in each Cohort 3, 4 and 5, which has been reflected in the Treatment Groups Table.
 
Figure 1 Study Design has been updated to add an additional Cohort and adjust the randomization ratio from 3:1 to 9:5 in Cohorts 3, 4 and 5.
 
The text has been edited to state that there will be 12 subjects in each Cohort 1 and Cohort 2 and 14 subjects in each of Cohorts 3, 4 and 5.
 
The wording has been updated such that sentinel dosing will take place in all Cohorts, except Cohort 3.
 
The additional Cohort (3) has been included in the rationale for Part B of the study.
 
The randomization ratio has been changed from 3:1 to 9:5 in Cohorts 3, 4 and 5. No sentinel dosing will take place in Cohort 3.
 
The title for Table 1 has been updated to Safety Events - Sample Size Sensitivity on Active Dose.
	
Except for the two sentinel subjects in Cohort 2, dosing was not completed in this Cohort because of the temporary halt, therefore this dose level will be repeated under the new Cohort designation of Cohort 3.
 
Cohort 3 will not require sentinel dosing since this was completed in the original dose level (Cohort 2).
 
The randomization ratio for Cohorts 3, 4 and 5 has changed from 3:1 to 9:5, with the overall number of subjects participating in each of these Cohorts increasing from 12 to 14. This will provide a more balanced review with the number of subjects on active and placebo.

2.2. Time and Events Table – Part B (Cohorts 2-5)
 
9.3.7. Holter
	
An additional row has been added to the SoA to include 24-hour Holter monitoring at screening.
 
A section has been added to include 24-hour Holter monitoring
	
24-hour Holter monitoring has been included in the screening visit for Cohorts 3, 4 and 5 to better understand the background telemetry patterns of each subject prior to the start of study drug.

Section # and Name	Description of Change	Brief Rationale
Monitoring	at screening.	

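### Part B cumulative compliance at each visit is divided by the whole 14-day dose count, so a perfect dosing record reads 50% on Day 7

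*SAP*

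**What the plan says.** The Treatment Compliance entry in SAP 10.6.2 has three parts that have to work together.

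- The formula: "Treatment Compliance = Number of Actual Doses / (Planned Treatment Duration in Days * Frequency" (the closing bracket follows). "Frequency is 2 for BID and 3 for TID".
- The denominator: "Planned Treatment Duration is defined as 1 day in Part A in each period and 14 days in Part B".
- The timing: "Cumulative compliance (since Day 1) at each visit will be calculated".

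The same entry allows compliance to exceed 100% where there is overdose. Under the separate Extent of Exposure entry the SAP adds: "If there are any treatment breaks during the study, exposure data will be adjusted accordingly". That sentence covers exposure and does not mention compliance.

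SAP 7.1 lists exposure and treatment compliance among the study population analyses and refers to Appendix 10 for the displays.

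**The concern.** The by-visit instruction and the defined denominator do not fit together. A cumulative figure on Day 7 should compare doses taken with doses due by Day 7. The only denominator written down is the full Part B course, which is 42 doses for TID. The entry's remark that values can pass 100% with overdose implies that a perfect record is meant to score 100%, and before Day 14 it cannot.

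What is at stake is the by-visit percentage itself. Two programmers working from this entry could derive 50% and 100% from the same Day 7 record, and the one who followed the definition exactly would have the misleading value.

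**Working it through.** The SAP gives no worked compliance figure, so there is nothing to reproduce. The check applies its own formula to a perfect record.

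**Inputs, all from SAP 10.6.2.** Planned duration is 14 days in Part B and 1 day per period in Part A. Frequency f is 3 for TID and 2 for BID. The Part B denominator is therefore 14 × 3 = 42 doses for TID and 14 × 2 = 28 for BID. The BID case now looks moot, because the note to the treatment table in SAP 5.1 says the Cohort 5 dose level was not required.

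**Formula as written, every dose taken, end of day d.** Compliance = (f × d)/(14 × f) = d/14. Frequency cancels.

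| Day | TID doses taken / 42 | As written | Doses taken / doses scheduled to date |
|---|---|---|---|
| 2 | 6/42 | 14.3% | 6/6 = 100% |
| 4 | 12/42 | 28.6% | 12/12 = 100% |
| 7 | 21/42 | 50.0% | 21/21 = 100% |
| 10 | 30/42 | 71.4% | 30/30 = 100% |
| 14 | 42/42 | 100% | 42/42 = 100% |

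After Day 14 no further doses are planned, so a perfect record stays at 100% at later visits.

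**Choice of cut-off.** The table assumes the visit value includes all of that day's doses. If Day 7 is cut before the first dose of the day, the formula as written gives 18/42 = 42.9%, so the shortfall does not depend on the end-of-day convention.

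**Real missed doses.** Suppose a TID participant has missed three doses by the end of Day 7. The to-date denominator gives 18/21 = 85.7%, which describes the adherence. The formula as written gives 18/42 = 42.9%, most of which is doses not yet due.

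**Part A.** With one planned day per period, a perfect record is 3/3 (TID) or 2/2 (BID) = 100%. The problem does not arise.

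**The case against.** **The intent is clear enough.** It can be argued that a cumulative figure since Day 1 at each visit can only mean doses due so far, so this is loose wording that a programmer would resolve correctly. That may well be the intent. But the SAP defines planned duration as 14 days and writes no second denominator, so the text points away from the sensible reading.

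**Nothing downstream uses it.** This stands. SAP section 4 bases no population on compliance, and no planned safety or PK analysis uses it. Table 1.12 names daily dose and days; Table 1.23 names daily dose, cumulative actual dose and days. Compliance appears only in the section headings of Appendix 10. Whether the sponsor's standard shells print a percentage cannot be seen from the documents. Protocol 7.5 has each dose given under supervision with a mouth check, so few missed doses are likely.

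**A stronger reading a reader might infer.** Protocol Amendment 02 describes cardiac arrhythmias "prompting a temporary dosing hold", and its Summary of Changes Table says: "Except for the two sentinel subjects in Cohort 2, dosing was not completed in this Cohort because of the temporary halt". From this one might conclude that the remaining Cohort 2 participants will be reported as non-compliant for doses never offered, and that missed and halted dosing cannot be told apart. The documents do not support that:

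- They do not say how many non-sentinel participants started dosing or when they stopped, and anyone never dosed is outside the Safety population.
- With no compliance threshold, nobody is classified as non-compliant.
- Table 1.14 and Listings 41, 42 and 51 give treatment status, reasons for withdrawal and for stopping treatment, and exposure, so stopped dosing can be separated from missed doses.
- Doses taken over the full planned course is a defensible overall measure. Ending the denominator at an imposed stop would be a preference, not a correction.

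**Conclusion.** The point holds for the by-visit calculation in Part B only. Read as written, SAP 10.6.2 understates cumulative compliance at every visit before Day 14 by the fraction of the course not yet due: by half at the end of Day 7, and by 100% − 14.3% = 85.7 percentage points at the end of Day 2. This rests on the literal text and on counting all doses through the end of the visit day.

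It is a stated rule that gives a wrong value, rather than a missing detail, but its consequence is small. No conclusion about safety or PK depends on it. No figure for Cohort 2 should be attached to it, because the numbers needed are not in the documents.

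**What to change.** In SAP 10.6.2, define by-visit cumulative compliance as doses taken from Day 1 through the visit divided by doses scheduled from Day 1 through the visit. State whether doses on the visit day itself count, and apply the same cut-off to numerator and denominator. Keep the 14-day denominator for the overall end-of-treatment value and label it as such.

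Optionally, add a sentence saying that a low overall value in a participant whose dosing was stopped by the sponsor or under the protocol reflects the stop, and show it beside the discontinuation reason and days of exposure.

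The cost is one line of SAP text, or two with the optional sentence, and a small change to the derivation program. Dose dates and times are already recorded, so no new data are needed.

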10.6.3. Safety

ECG Parameters

RR Interval

IF RR interval (msec) is not provided directly, then RR can be derived as:
 If QTcF is machine read, then:

$$RR = \left[\left(\frac{QT}{QTcF} \right)^3 \right] * 1000$$

• If ECGs are manually read, the RR value preceding the measurement QT interval should be a collected value THEN do not derive.

Corrected QT Intervals

- When not entered directly in the eCRF, corrected QT intervals by Fridericia's (QTcF) formulas will be calculated, in msec, depending on the availability of other measurements.
- IF RR interval (msec) is provided then missing QTcF will be derived as:

$$QTcF = \frac{QT}{3\sqrt{\frac{RR}{1000}}}$$

Laboratory Parameters

• If a laboratory value which is expected to have a numeric value for summary purposes, has a nondetectable level reported in the database, where the numeric value is missing, but typically a character value starting with '<x' or '>x' (or indicated as less than x or greater than x in the comment field) is present, the number of significant digits in the observed values will be used to determine how much to add or subtract in order to impute the corresponding numeric value.

- Example 1: 2 Significant Digits = '< x ' becomes x 0.01
- Example 2: 1 Significant Digit = '> x' becomes x + 0.1
- Example 3: 0 Significant Digits = 4×1

10.7. Appendix 7: Reporting Standards for Missing Data

10.7.1. Premature Withdrawals

Element	Reporting Detail
General	 Participant study completion (i.e. as specified in the protocol) was defined as one who has completed all phases of the study including the last scheduled procedure shown in the SoA (see Appendix 2). Withdrawn participants may be replaced in the study. Additional replacement participants may be randomized to guarantee that sufficient participants are treated with GSK2982772 at any given dose before escalating to the following dose. Replacement participants will be assigned to the same treatment sequence (Cohort 1) or treatment (Cohorts 2-5) but have different subject numbers and randomisation numbers assigned. All available data from participants who were withdrawn from the study will be listed and all available planned data will be included in summary tables and figures, unless otherwise specified.
Liver Chemistry Stopping Criteria	 Discontinuation of study treatment for abnormal liver tests is required when: in the presence of abnormal liver chemistries not meeting protocol-specified stopping rules, the investigator believes study treatment discontinuation is in the best interest of the participant. ALT ≥ 3 x ULN. Note: Refer to Appendix 7 of the protocol for details of the required assessments if a participant meets the above criteria.
QTc Stopping Criteria	 A participant that meets either bulleted criterion based on the average of triplicate ECG readings will be withdrawn from study treatment: QTcF > 500 msec Change from baseline: QTcF > 60 msec
Nervous System Stopping Criteria	 A participant will be withdrawn from the study if: A Grade 3 or greater CTCAE Nervous System finding is observed or a significant neurologic change from a participant's baseline physical examination is observed. Any adverse event included in the CTCAE for Nervous System, which is also considered to be clinically significant by the Principal Investigator, will be reviewed for potential participant withdrawal.

10.7.2. Handling of Missing Data

Element	Reporting Detail
General	 Missing data occurs when any requested data is not provided, leading to blank fields on the collection instrument: These data will be indicated by the use of a "blank" in participant listing displays. Unless all data for a specific visit are missing in which case the data is excluded from the table. Answers such as "Not applicable" and "Not evaluable" are not considered to be missing data and should be displayed as such.
Outliers	Any participants excluded from the summaries and/or statistical analyses will be documented along with the reason for exclusion in the clinical study report.

Element	Reporting Detail
General	Partial dates will be displayed as captured in participant listing displays.
Adverse Events	 The eCRF allows for the possibility of partial dates (i.e., only month and year) to be recorded for AE start and end dates; that is, the day of the month may be missing. In such a case, the following conventions will be applied for calculating the time to onset and the duration of the event: Missing Start Day: First of the month will be used unless this is before the start date of study treatment; in this case the study treatment start date will be used and hence the event is considered On-treatment as per Appendix 4: Study Phases and Treatment Emergent Adverse Events. Missing Stop Day: Last day of the month will be used, unless this is after the stop date of study treatment; in this case the study treatment stop date will be used.
	 Completely missing start or end dates will remain missing, with no imputation applied. Consequently, time to onset and duration of such events will be missing.
Concomitant Medications/ Medical History	 Partial dates for any concomitant medications recorded in the CRF will be imputed using the following convention: If the partial date is a start date, a '01' will be used for the day and 'Jan' will be used for the month If the partial date is a stop date, a '28/29/30/31' will be used for the day (dependent on the month and year) and 'Dec' will be used for the month. The recorded partial date will be displayed in listings.

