9.1.1. Time Period and Frequency for Collecting AE and SAE Information

- All SAEs will be collected from the start of treatment until the follow-up visit at the time points specified in the SoA (Section 2). However, any SAEs assessed as related to study participation (e.g., study treatment, protocol-mandated procedures, invasive tests, or change in existing therapy) or related to a GSK product will be recorded from the time a subject consents to participate in the study.
- All AEs will be collected from the start of treatment until [the follow-up visit] at the time points specified in the SoA (Section 2).

- Medical occurrences that begin before the start of study treatment but after obtaining informed consent will be recorded on the Medical History/Current Medical Conditions section of the CRF not the AE section.
- All SAEs will be recorded and reported to the sponsor or designee immediately and under no circumstance should this exceed 24 hours, as indicated in [Appendix 4](#). The investigator will submit any updated SAE data to the sponsor within 24 hours of it being available.
- Investigators are not obligated to actively seek AEs or SAEs in former study participants. However, if the investigator learns of any SAE, including a death, at any time after a participant has been discharged from the study, and he/she considers the event to be reasonably related to the study treatment or study participation, the investigator must promptly notify the sponsor.
- The method of recording, evaluating, and assessing causality of AEs and SAEs and the procedures for completing and transmitting SAE reports are provided in [Appendix 4](#).

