10.4. Appendix 4: Study Phases and Treatment Emergent Adverse Events

10.4.1. Study Phases

Assessments and events will be classified according to the time of occurrence relative to the start and/or stop date/time of the study treatment within the period for Part A and the start and/or stop date/time of the study treatment for Part B.

Study Phase	Definition
Pre-Treatment	Date/Time ≤ Study Treatment Start Date/Time
On-Treatment	Study Treatment Start Date/Time < Date/Time ≤ Study Treatment Stop Date/Time
Post-Treatment	Date/Time > Study Treatment Stop Date/Time

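### The rule for a missing AE stop day caps the end at the treatment stop date with no floor at onset, so events starting on a later date get an end before their start and persisting events are cut short

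*SAP*

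**What the plan says.** The Adverse Events row for missing and partial dates in SAP 10.7.2 covers events recorded with month and year only. It states its purpose: "the following conventions will be applied for calculating the time to onset and the duration of the event". When only the stop day is absent, the default reads: "Last day of the month will be used, unless this is after the stop date of study treatment". Where month-end is the later of the two, a cap replaces it: "in this case the study treatment stop date will be used". The row has no exception for events that begin after treatment and no condition tying the imputed end to the start. End dates that are missing altogether are left missing. The same section adds: "Partial dates will be displayed as captured in participant listing displays".

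Events after dosing are expected. Protocol 9.1.1 sets the collection period ("All AEs will be collected from the start of treatment until"), and its end point is the follow-up visit, which the synopsis places 7 to 14 days after the last dose. SAP 10.4.1 defines a post-treatment phase as "Date/Time > Study Treatment Stop Date/Time", and SAP 10.4.2 counts an onset up to one day after the treatment stop date as treatment emergent.

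On treatment length, SAP 10.6.2 says: "Planned Treatment Duration is defined as 1 day in Part A in each period and 14 days in Part B". For study phases, SAP 10.4.1 refers to the "start and/or stop date/time of the study treatment within the period for Part A". The imputation row does not say whether its own stop date is per period or per study.

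**The concern.** A rule written to derive AE duration should not return an end date earlier than the start. The cap treats the last dose as the latest date on which an AE can end, while the protocol collects AEs well past it. Partial stop dates are most plausible after discharge (Day 4 of a Part A period, Day 17 in Part B), because AEs are reviewed daily while participants are in the unit. The cap therefore bites where imputation is most likely to be needed. At stake is the derived duration of late-starting or persisting events, in a study whose primary objective is safety and tolerability.

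**Working it through.** The plan states no figure on this point, so there is none to reproduce. The check is of the rule's logic.

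**Inputs**
- S = treatment stop date. Part B: Day 14 for a completer. Part A: Day 1 of the period, if taken within the period (SAP 10.4.1, one dosing day per period).
- O = onset date, taken as known. T = true end, with T ≥ O.
- M = last day of the recorded stop month, so M ≥ T.
- Imputed end E = earlier of M and S (SAP 10.7.2).
- Follow-up ends no later than S + 14 days (Protocol synopsis).

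**Onset after the last-dose date (O > S).** M ≥ T ≥ O > S, so the cap always applies and E = S < O.

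**Onset on or before the last-dose date, end after it (O ≤ S < T).** M ≥ T > S, so E = S < T. The event is cut short, but E is not before O.

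**Enumeration.** This used 365 consecutive Day 1 dates, onsets from Day 1 to S + 14, and true ends 0 to 14 days after onset but no later than S + 14. The counts show how the rule behaves, not how often such events will occur.
- Onset after S: E precedes onset in 38,325 of 38,325 scenarios in each part. In 12,180 of these per part, E also falls outside the recorded stop month.
- Onset on S: E equals onset in 5,475 of 5,475 in each part. It is earlier than the true end in 5,110 (365 × 14).
- Part B, onset before S: E never precedes onset. It is earlier than the true end in 33,215 of 71,175 (365 × 91 = 33,215), which are exactly the scenarios that outlast S.
- Part A, stop date within the period: E is Day 1 in all 43,800 (38,325 + 5,475).

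**Duration.** Taking D = E - O + 1 (assumed; the SAP uses a plus-one for exposure and study day but gives no formula for AE duration):
- Part A, within-period stop date: onset Day 2 gives 1 - 2 + 1 = 0; onset Day 3 gives 1 - 3 + 1 = -1.
- Part B: onset Day 15 gives 14 - 15 + 1 = 0; onset Day 20 gives 14 - 20 + 1 = -5.

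Part A Day 2 and Part B Day 15 are one day after the stop date, so those events are treatment emergent. Part B Day 20 lies inside the collection window, since follow-up falls between Day 21 (14 + 7) and Day 28 (14 + 14).

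**Part A with a study-level stop date.** Dosing days were assumed 8, 14 or 21 days apart. Period 1 events started on Days 1 to 4 and ended 0 to 4 days later (7,300 scenarios per spacing). E never preceded onset and equalled Day 1 in only 12 scenarios at each spacing. It equalled the study-level stop date in 4,300, 1,420 and 0 respectively. Last-period events starting after their dosing date would still get an end before onset.

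**The case against.** The strongest reply is that nothing reported is shown to change. The imputation serves time to onset and duration only. The planned AE tables (2.1 to 2.6 and 2.21 to 2.26) and figures (2.1 and 2.4) cover counts, intensity, relatedness, seriousness, discontinuation and relative risk; none is titled for duration. The treatment-emergent flag uses onset, and listings show the date as recorded. This stands. Whether the AE listings carry a duration column depends on display shells not in the documents. A reader might infer that the safety tables will make late events look shorter; the documents identify no table that would.

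Two other broader readings also fail. A reader might suppose that every event after a dose gets a reversed date. An event starting later on the last dosing date gets an end equal to its onset date, which may be too early but is not reversed. If the start day is also missing and the start month is the month of the last dose, the start is imputed to the first of the month or to treatment start, so the end does not precede it.

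A reader might also take it as settled that Part A events are forced to end on Day 1. That follows only if the stop date is the within-period one. SAP 10.4.1 supports this for study phases, but 10.7.2 is silent, and the one-day figure in 10.6.2 defines planned duration for compliance, not a stop date.

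None of this rescues the rule for a known onset date after the applicable stop date.

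**Conclusion.** The rule is wrong as written, but the consequence is small. For any AE with a missing stop day and a known onset date after the last-dose date, the imputed end precedes onset without exception. For AEs that start on or before that date and outlast it, derived duration is truncated at the last dose. In Part A the imputed end is Day 1 of the period, conditional on the within-period stop date.

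The values of -1 day and -5 days rest on the assumed plus-one formula; the order of the dates does not. The documents give no basis for estimating how many AEs will have a partial stop date. The effect is confined to derived duration for those events, and nothing in the documents shows that AE incidence, treatment-emergent classification or any primary safety conclusion would change.

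**What to change.** Remove the treatment-stop cap from the missing stop day rule. Replace it with: the earlier of the last day of the recorded month and the participant's last contact date, including any extended AE follow-up, and never earlier than the AE start date or the first day of the recorded stop month.

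Last contact is preferable to the follow-up visit because Protocol 9.1.3 follows SAEs and AEs of special interest until they resolve or stabilise, possibly beyond that visit. The month floor keeps the imputed date consistent with what was recorded. With the cap gone, the Part A ambiguity no longer affects the imputed stop date.

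A simplified version, with S + 14 days standing in for last contact and a floor at onset, gave no end before onset and none before the true end in either part of the enumeration. The same SAP section already imputes concomitant medication stop dates without a treatment-date cap. The cost is one sentence in the SAP and the matching programming change, with no effect on data collection or planned displays.
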